Varying methods of IANL and immediate implant placements that have used drills, burs, or saws have been reported [26, 27]. Disturbances in postoperative neurosensory function of the IAN are common. The risk of IAN morbidity created some controversy, which resulted in the limited use of this classic technique [28]. To tackle problems in edentulous instances, especially those with atrophic mandibles, various surgical procedures utilizing osseointegrated implants have been devised [29]. Onlay bone grafting, a prevalent approach, necessitates a secondary surgical site and entails hazards including graft resorption, infection, and the requirement for two surgical procedures, thereby prolonging the entire treatment duration [29-31]. The bone quality in the posterior mandible is generally lower than that of the anterior area. Utilizing short implants to circumvent the mandibular canal often results in initial implant anchorage that is monocortical and comparatively unstable [32].

The key benefits of IAN relocation encompass the utilization of standard-length implants with bicortical anchorage, hence augmenting primary stability, which is essential for effective osseointegration. Implants accompanied by nerve relocation have a reduced risk of bone loss when compared to short implants implanted under analogous conditions [33]. In instances when the vertical bone height is below 5 mm—insufficient for even small implants—IAN repositioning is the advised procedure [34]. This treatment enhances resistance to occlusal stresses and guarantees an appropriate implant-to-prosthesis connection. In comparison to bone grafting, IAN relocation presents multiple advantages: it can be executed under local anesthetic, eliminates the need for a donor site, incurs cheaper expenses, and is linked to diminished morbidity [14, 35]. The present study aimed to investigate the efficacy of the IANL procedure for dental implants in the atrophied mandibles.

Patients and Methods:

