This is a prospective randomized clinical trial. The study was carried out in patients with posterior mandibular atrophies among selected cases from patients attending Faculty of Dentistry dental polyclinics and some private dental clinics in Sana'a City from 10 July 2024 to 20 April 2025. The minimal calculated sample size was nine cases (G-power sample calculator; Effect size, 99.99; α err prob, 0.05; Power, 0.80; and Df, 7) [36]. The age of patients was above 18 years, according to [36]. Patients included in the study were those who have a bone height above the IAN that ranged from 0.5 to 7.0 mm and patients with bone width less than 5 mm in the planned dental implant sites. All patients were informed about alternative treatments and given information regarding all steps of the procedure, the risks of the surgery, and possible postoperative neurosensory dysfunction. All explanations were given to the patients verbally and in a written manner. Patients with active infections, uncontrolled diabetes, or a history of radiotherapy, chemotherapy, or oral cancer surgery were excluded from this study. Demographic data (name, age, gender, occupation, address, phone number, and habits) were collected using a preformed questionnaire. Present and past medical and dental history was also recorded for all patients. All patients received a thorough dental examination (extra-oral and intra-oral examination) in dental clinics using a dental mirror, ball-tipped WHO dental probe, and dental tweezers. Sterile examination tools by autoclave class B were used. Clinical examination included oral health and oral hygiene status, interarchdistance, dimensions of edentulous ridge, and soft tissue condition. Panoramic radiographs were taken to assess the condition of the patients' teeth and jawbone, as well as to detect any oral infections requiring treatment. These images also served as baseline documentation for comparison before and after treatment. CBCT revealed significant vertical and horizontal bone loss (bone quantity) and bone density (bone quality) in the mandibular premolar and molar areas, with the residual bone above the IAN ranging from 0.5 to 7.0 mm. All cases' mandibles were classified as class V (flat ridge form, inadequate in height and width) or class VI (depressed ridge form, with some basilar loss evident) according to the Howell-Cawood classification [5]. All patients were provided written

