Testing of nerve function and implant success rate during the scheduled follow-up visits was scheduled on the day after the procedure and at 1, 3, and 6 months immediately following the surgery [40]. Patients were asked about pain and neurosensory disturbance classified as positive (including paresthesia, dysesthesia, and hyperesthesia) or negative (such as hypoesthesia and anesthesia). The incidence and duration of neurosensory disturbance were evaluated by the light touch test using cotton or gauze. A cotton tip applicator is used to determine sensation (Static Touch Detection Tests), and a pinprick test is done with an insulin needle and the tip of an explorer probe at predetermined intervals of time. Neurosensory evaluation was carried out on the 1st and 7th postoperative days and every month thereafter for up to 6 months. The areas of impaired nerve function were mapped and followed during each follow-up appointment. The evaluation of nerve function was performed by two calibrated examiners. [34] The implant success rate was done by primary stability during insertion by ratchet, then X-rays (panorama and CBCT) were taken at 3 months and 4 months after implant insertion to check for marginal bone loss (MBL). The degree of osseointegration of the implants was determined by examining whether or not the implants were both painless and immobile when under torque and while

loading and whether or not any pathology was detected in the X-rays during the examination [34].

Abutments and prosthodontic procedures:

In this study, all patients received prosthetic rehabilitation using AnyRidge (MegaGen) implants with multi-unit abutments to ensure a predictable and efficient restorative phase. The multi-unit abutments, designed by the manufacturer, were selected based on implant angulation and soft tissue thickness, with both straight and angled options (15° and 25°) and various collar heights available to accommodate individual anatomical variations. These abutments helped standardize the prosthetic platform, simplify the restoration delivery, and improve long-term outcomes. All prostheses were cement-retained, except for one case where a screw-retained restoration was employed. The use of multi-unit abutments played a key role in managing implant angulation and facilitating a smooth and accurate prosthodontic alignment.

Data management and statistical analysis:

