All data were collected and then analyzed using statistical software (SPSS Version 27; SPSS Inc., Chicago, USA). Descriptive analyses were performed as frequency and proportion for categorical variables and the mean and standard deviation of quantitative variables. Analytical statistics were performed to find out the association between variables (demographic characteristics, neurosensory disturbance, and success rate of implant) with IANL. Non-parametric tests were done to measure the differences between pre- and post-times of operation (Fridman and Wilcoxon tests). $P < 0.05$ was considered statistically significant.

List of Abbreviations:

Abbreviations

Definition

IAN

Inferior Alveolar Nerve

IANL

Inferior Alveolar Nerve Lateralization

IANT

Inferior Alveolar Nerve Transposition

RRR

Residual Ridge Resorption

CBCT

Cone Beam Computed Tomography

ND

Neurosensory Disturbances

MC

Mandibular Canal

PRF

Platelet-Rich Fibrin

MBL

Marginal Bone Loss

Declarations:

Ethics approval and consent to participate: The study design adhered to the tenets of the Declaration of Helsinki and was approved by the Medical Research Ethics Committee in the Faculty of Medicine at Sana'a University; ethical approval was obtained (Approval Number: OMFS:14/06/2024). Detailed explanation of the procedures was provided for all participants. Verbal and written consent were obtained from all participants; all patients agreed to be involved in the study.

Clinical trial number: not applicable.

Consent for publication: NA

Availability of data and materials: The authors confirmed that the raw data that support the findings of this study are available from the corresponding author upon reasonable request.

Competing interests: The authors declare that they have no competing interests.

Funding: The study was self-funded by the authors.

Authors' contributions: HS & YA performed the surgical interventions and collected data from the patients and drafted the manuscript. MA performed the conceptualization of the study and was a major contributor in writing the manuscript. YA, AA, and TA revised the clinical work and the draft manuscript. All authors read and approved the final manuscript.

Acknowledgements: the authors thank all the patients included in the study as well as the Department of Oral and Maxillofacial Surgery in the Faculty of Dentistry, Sana'a University.

References:

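### Duration of neurosensory disturbance is an outcome, but testing ends at month 6 and the plan has no rule for disturbance still present then

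*Combined protocol and SAP*

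**What the plan says.** All references are to the combined protocol and SAP.

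- **Outcome.** Post-operative follow-up names both incidence and duration of ND: "The incidence and duration of neurosensory disturbance were evaluated by the light touch test using cotton or gauze".
- **Testing schedule.** The same section lists nerve testing twice. Testing of nerve function together with implant success "was scheduled on the day after the procedure and at 1, 3, and 6 months immediately following the surgery". Further on: "Neurosensory evaluation was carried out on the 1st and 7th postoperative days and every month thereafter for up to 6 months". Neither list goes beyond month 6.
- **What is recorded.** "The areas of impaired nerve function were mapped and followed during each follow-up appointment".
- **Analysis.** Data management and statistical analysis states: "Descriptive analyses were performed as frequency and proportion for categorical variables and the mean and standard deviation of quantitative variables". It adds Friedman and Wilcoxon tests for pre- versus post-operative differences. It does not name ND duration, and gives no censoring rule and no time-to-event method.
- **Importance of the outcome.** The Background says of nerve injury: "The risk of IAN morbidity created some controversy, which resulted in the limited use of this classic technique". Patients and Methods says patients were told of "the risks of the surgery, and possible postoperative neurosensory dysfunction".

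**The concern.** A patient who still has ND at month 6 has no observed duration; it is known only to exceed 6 months. The plan does not say how that patient enters the result. The only summary it states for a quantitative variable needs a number for each patient, so there are two ways to apply it:

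- **Drop the patient.** The mean then describes only those who recovered.
- **Enter 6 months.** The mean then records a floor for the patient.

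In either case the patients who matter most for harm are left out or only partly counted, on the outcome that the plan itself gives as the reason for the technique's limited use. With about nine patients, one or two such cases can move the result. There is a smaller gap as well: testing places recovery only between two visits, and no rule says which date is used.

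**Working it through.** **Inputs.** Nine patients is the minimum sample size in Patients and Methods. The visit lists are day 1 and months 1, 3, 6 (four visits), and days 1 and 7 then months 1 to 6 (eight visits). The plan states no figure for duration or persistence of ND, so there is none to reproduce. Recovery times below are assumptions, shown as a range.

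**Step 1: no recovery model.** Suppose all nine patients have ND, seven recover at months 1, 1, 2, 2, 3, 3, 4 (sum 16), and two do not recover by month 6.

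- Two dropped: 16/7 = 2.29 months.
- Two entered as 6: (16 + 12)/9 = 3.11 months.
- Both in fact last to month 12: (16 + 24)/9 = 4.44 months.

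In general, with k of nine unresolved, entering 6 understates the mean by k/9 month for each further month that their ND lasts.

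**Step 2: assumed exponential recovery, all patients with ND, eight-visit list.** With median m, the true mean is m/ln 2, the share unresolved at month 6 is 0.5^(6/m), and the mean time with ND within 6 months is (m/ln 2) × (1 − share unresolved). For m = 3: 3/0.693 = 4.33; 0.5² = 0.25; 4.33 × 0.75 = 3.25. The recorded mean is the sum over visit intervals of the probability of recovery in the interval times the assigned date, which is either the first normal visit or the interval midpoint. Each pair below is dropped / 6 entered, in months.

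| Median | True mean | Unresolved at month 6 | Mean within 6 months | First-normal-visit dating | Midpoint dating |
|---|---|---|---|---|---|
| 1 | 1.44 | 1.6% | 1.42 | 1.78 / 1.85 | 1.39 / 1.46 |
| 2 | 2.89 | 12.5% | 2.52 | 2.49 / 2.93 | 2.05 / 2.55 |
| 3 | 4.33 | 25% | 3.25 | 2.79 / 3.59 | 2.34 / 3.26 |
| 6 | 8.66 | 50% | 4.33 | 3.12 / 4.56 | 2.66 / 4.33 |

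At median 6 both treatments fall far below the true mean. At median 1 with first-normal-visit dating both lie above it. With midpoint dating, entering 6 almost reproduces the mean within 6 months.

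**Step 3: how likely the problem is to arise.** The chance that at least one of nine is unresolved at month 6 is 1 − (1 − p)^9, where p is the share of all patients unresolved. If all nine develop ND, it is 13%, 70%, 92% and 99.8% at medians 1, 2, 3 and 6. If half do (p halved), it is 7%, 44%, 70% and 92%.

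**Step 4: the two visit lists.** The four-visit list is contained in the eight-visit list. Over medians 0.5 to 6 months, using four visits instead of eight raises the mean by 0.34 to 0.67 month with first-normal-visit dating, but by only 0.02 to 0.13 month with midpoint dating. For example, recovery at 3.5 months would be dated 6 or 4 at the first normal visit.

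**Step 5: precision of a month-6 proportion.** Clopper-Pearson 95% intervals are 0 to 33.6% for 0 of 9, 0.3 to 48.2% for 1 of 9, and 2.8 to 60.0% for 2 of 9.

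**The case against.** The strongest reply is that the plan never says ND duration will be summarised by mean and SD. That sentence is generic. The same section provides frequencies and proportions for categorical variables and Friedman and Wilcoxon tests across time points, and ND is tested and mapped at each visit. ND status by visit is therefore a natural reading, under which a patient impaired at month 6 is simply counted as impaired. This stands in part: by-visit reporting is permitted. But the plan does not commit to it, and it does not settle how duration, a named outcome, is derived.

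Three stronger readings are tempting, and the documents do not support them.

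- **A reader might infer that the plan always makes ND look shorter than it is.** It depends on recovery speed and dating: at median 1 with first-normal-visit dating the recorded mean is too long. Entering 6 is also a legitimate quantity if labelled as mean time with ND within 6 months. The largest gaps come from the assumed tail beyond follow-up.
- **A reader might infer that a mean with unresolved patients dropped never responds to how many fail to recover.** That holds only if the recovered patients' times are held fixed. In the table it rises from 1.78 to 3.12 as the unresolved share rises.
- **A reader might infer that the two visit lists flatly contradict each other.** They are nested. The first covers nerve function and implant success together; the second is specific to neurosensory evaluation and probably governs, though the text does not say so.

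**Conclusion.** The concern holds in a limited form. Duration of ND is a named outcome, observation stops at month 6, and no rule covers ND still present at the last visit. If the general mean-and-SD rule is applied to duration, it either omits the unresolved patients or estimates a different quantity from the one named.

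The size depends on a recovery rate that the documents do not give. Under the exponential assumption, with first-normal-visit dating, a true mean of 8.66 months would be reported as 3.12 or 4.56 when the median is 6. At a median of 2, entering 6 gives 2.93 against 2.89, so no understatement remains. The chances of at least one unresolved patient rest on nine patients, a stated minimum, and on the assumed incidence of ND. If nobody is impaired at month 6, only the dating question remains. The visit-list discrepancy is minor.

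This should be corrected because it affects how a central harm is reported and the correction is cheap. Confidence is medium, since the number unresolved is unknown.

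**What to change.** 1. Do not use mean and SD as the summary of ND duration. Report the number with ND over the number assessed at each visit and, at month 6, the proportion still impaired with an exact 95% CI.
2. Define recovery from the tests already listed in Post-operative follow-up, including how the two examiners' findings combine. For each patient with ND, record the last impaired and first recovered visits and treat recovery as lying between them. Right-censor ND still present at the last assessment, whether that is month 6 or earlier. An interval-censored (Turnbull) curve is optional at this sample size. If a mean is kept, label it mean time with ND within the first 6 months and show the number unresolved beside it.
3. As a minor point, reconcile the two lists of nerve-testing visits into one.

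**Cost.** A text correction and a table of counts. Impaired areas are already mapped at each appointment, so no new visits or tests are needed. The downside is imprecision: with about nine patients the intervals in Step 5 apply, and a median time to recovery may not be reached.

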[13]. Numerous therapeutic modalities have been suggested in the literature to tackle this issue, including the insertion of short implants, sandwich osteotomy, vertical ridge augmentation, and distraction osteogenesis. An alternative approach involves exposing the Inferior Alveolar Nerve (IAN) by laterally displacing it from the canal through nerve lateralization or transposition [14, 15].

The inferior alveolar nerve, a major branch of the mandibular nerve, innervates the mandibular teeth, periodontium, lower lip, and jaw. It traverses the lower jaw via the mandibular foramen, encased in firmly bound connective tissue, and subsequently proceeds downward and forward within the mandibular canal, typically situated behind the root apex [13]. Within the mandibular canal, it accompanies the inferior alveolar artery (IAA), vein, and lymphatic vessels, forming the inferior alveolar neurovascular bundle [16, 17]. The assessment of the infra-alveolar nerve canal's relative position and its association with mandibular anatomical landmarks can be therapeutically advantageous in reducing the risk of surgical problems, such as nerve damage, that may arise following invasive mandibular surgeries. Furthermore, the evaluation of bone height and width includes the Cone Beam Computed Tomography (CBCT) study of the trajectory and location of the mandibular canal [18].

Two techniques pertain to the alveolar nerve; the initial technique involves inferior alveolar nerve transposition (IANT) via a bone window fashioned in the cortical bone of the jaw, posterior to the mental foramen, excluding it. The second approach incorporates the mental foramen inside the established bone window and is referred to as IANL [19, 20]. In contrast to graft-based reconstruction methods, the lateralization procedure eliminates the need for donor sites, thereby reducing patient morbidity, lowering expenses, facilitating the immediate placement of long implants (as it utilizes all available jawbone), and averting a six- to eight-month waiting period for treatment [21]. IAN lateralization is a complex surgical operation that necessitates the exposure of the neurovascular bundle from its dense bone compartment and sufficient retraction, with the prompt implantation of an implant. This operation necessitates

substantial clinical expertise, anatomical understanding, and the capability to address any complications [22-25].

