Nerve lateralization:

The cortical bone block is removed with the aid of a periosteal elevator and kept hydrated in saline solution. After osteotomy, the mandibular canal is exposed, and the IAN is gently manipulated to remove cancellous bone fragments that may hinder a full mobilization of the IAN. The nerve was retracted laterally by a specially fabricated instrument (elastic tape), according to [39], and carefully protected in a way to allow implant bed preparation through its medial surface up to the desired bone depth.

Implant placement:

The AnyRidge MegaGen dental implants were then inserted to the ideal locking depth, in accordance with the predetermined position and direction. The selected implants should be long enough to allow anchorage in the basal cortical bone of the mandibular body and provide adequate locking and stability [38].

Inlay autogenous bone graft repositioned:

The inner surface of the previously harvested bone block can be contoured using specialized piezoelectric tips to ensure precise adaptation to the defect site at the end of the surgery, promoting close bone-to-implant contact. This approach results in an optimal inlay autogenous bone graft, which is the basis for the technique's name. The bone block is then repositioned and secured in its original location to effectively close the bone defect [38]. In the final step, soft tissues were carefully approximated and sutured using interrupted stitches with 3-0 silk sutures.

Post-operative care:

Patients received standard postoperative care instructions and were advised to avoid chewing on the operated side. A soft and liquid diet was recommended during the implant osseointegration period. Anti-inflammatory drugs, analgesics, and antibiotics were administered according to established protocols. Neurostimulatory drugs (methylcobalamin) can be administered shortly after surgery, depending on the patient's sensory perception and the IAN trauma extension. Sutures are removed only after confirmation of edge repair, usually 12 days after surgery. Implants are loaded 90 to 120 days after insertion [38].

Post-operative follow-up:

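### Nerve pain can fail a sound implant: the osseointegration check requires a painless implant in the territory of the nerve being mobilised, and success is not also reported without pain

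*Combined protocol and SAP*

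**What the plan says.** Post-operative follow-up holds two statements about how implants are judged.

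- The first reads "The implant success rate was done by primary stability during insertion by ratchet", followed by X-rays at 3 and 4 months for marginal bone loss. Neither measure has a cut-off.
- The second determines the degree of osseointegration by "examining whether or not the implants were both painless and immobile when under torque and while" and continues "loading and whether or not any pathology was detected in the X-rays during the examination". It names three conditions: no pain, no mobility, no radiographic pathology.

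Four other statements bear on the pain condition.

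- Background says that the inferior alveolar nerve (IAN) "innervates the mandibular teeth, periodontium, lower lip, and jaw". It also says: "Disturbances in postoperative neurosensory function of the IAN are common".
- Nerve lateralization describes how the IAN is handled while the implant bed is prepared: "The nerve was retracted laterally by a specially fabricated instrument (elastic tape").
- Post-operative care puts loading between day 90 and day 120.
- Post-operative follow-up assesses neurosensory disturbance (ND) on days 1 and 7 and then monthly to 6 months. "Patients were asked about pain and neurosensory disturbance classified as positive" (dysesthesia and hyperesthesia are among the examples) or negative (anesthesia, hypoesthesia).

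Patients and Methods adds one modified questionnaire that registers both ND and implant success. Data management and statistical analysis lists both as variables, in an "association between variables (demographic characteristics, neurosensory disturbance, and success rate of implant) with IANL".

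**The concern.** One of the three conditions is what the patient feels at the implant, and the operation can change that feeling. The plan expects both painful and numbing disturbance, and it applies the check while ND is still being followed. It has no rule for deciding whether pain on torque or loading comes from the implant or from the nerve, and it does not say how to score the pain condition at a numb site. It has no success figure that leaves pain out.

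The stated aim is the efficacy of nerve lateralization for implants. Sensory disturbance is a recognised harm of the procedure, and a working implant is its purpose. If nerve pain fails a sound implant, the same harm is counted twice: once as ND, and again, unseen, as lost implant success. A reader of the results could not tell an implant that failed to integrate from an integrated implant beside a painful nerve.

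**Working it through.** The plan gives no rate of ND, of pain at the implant or of implant failure, so there is no figure to reproduce. The check is on the logic of the criterion, followed by illustrations on assumed values.

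**Step 1. Does the check overlap with ND in place and time?** In place, yes: Background puts the jaw in the IAN's territory, and Nerve lateralization has that nerve retracted during preparation of the implant bed. In time, yes: loading at days 90 to 120 is about months 3 to 4, inside ND follow-up to month 6.

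**Step 2. What can the nerve do to the result?** The criterion is a conjunction, so all three conditions must hold.

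| Implant | Nerve | Painless | Immobile | X-ray clear | Result |
|---|---|---|---|---|---|
| Sound | Normal | yes | yes | yes | pass, correct |
| Sound | Neuropathic pain | no | yes | yes | **fail, false** |
| Failed, mobile or visible on X-ray | Numb | yes | at least one no | (see left) | fail, correct |
| Failed, pain the only sign | Numb | yes | yes | yes | **pass, false** |

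Nerve pain alone is enough for a false fail. A false pass needs both numbness and a failed implant that shows by neither mobility nor X-ray.

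**Step 3. How do the two directions compare?** Let π be the share of implants truly integrated, b the share of sound implants with neuropathic pain, a the share of sites that are numb, and s the share of true failures caught by mobility or X-ray. Pain catches the remaining failures unless the site is numb. Then

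observed pass rate = π(1 − b) + (1 − π)(1 − s)a.

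All four values are assumptions.

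- Nerve pain only (a = 0):
  - π = 0.90: 0.90 × 0.90 = 0.81 at b = 0.10, and 0.90 × 0.80 = 0.72 at b = 0.20.
  - π = 0.95: 0.95 × 0.90 = 0.855 and 0.95 × 0.80 = 0.76.
  - The fall is 9 to 19 percentage points.
- Numbness only (b = 0), half of failures showing only as pain (s = 0.5):
  - π = 0.90: 0.90 + 0.10 × 0.5 × 0.20 = 0.91 at a = 0.20, and 0.92 at a = 0.40.
  - π = 0.95: 0.955 and 0.96.
  - The rise is 0.5 to 2 points.
- Numbness only, every failure caught by mobility or X-ray (s = 1): the second term is zero and nothing changes.

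The upward effect can never exceed (1 − π)(1 − s), which is 0.10 × 0.5 = 0.05 at π = 0.90 and s = 0.5, even if every site is numb.

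**Step 4. What does one patient weigh?** Patients and Methods gives a minimum of nine cases. Suppose all nine have sound implants. One patient failed by nerve pain gives 8/9 = 88.9%, a drop of 1/9 = 11.1 points. Two give 7/9 = 77.8%, with no implant lost. With N patients the step is 1/N, so it shrinks if more are enrolled.

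**Step 5. Would simply deleting pain be better?** Not clearly. Without the pain condition the pass rate is π + (1 − π)(1 − s). At s = 0.5 this is 0.95 for π = 0.90 and 0.975 for π = 0.95, which overstates true integration by 5 and 2.5 points. Each version errs in its own direction, which is the reason to show both.

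**The case against.** Several arguments on the other side are sound.

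- **Numbness.** A reader might infer that numb patients pass whatever the state of the implant, so that success is biased upward in them. The documents do not support that, because immobility and clear X-rays are still required. The Surgical protocol also blocks the lingual and long buccal nerves, so IAN numbness alone need not silence the whole site. This stands.
- **Status of the criterion.** A reader might take the sentence as the plan's implant-success rule and conclude that the efficacy claim rests on it. The sentence concerns the degree of osseointegration; the preceding one ties success to ratchet stability and X-rays, and the questionnaire registers success as well. No single rule is stated and no main outcomes are named. This stands, although the other measures have no cut-offs, so this remains the nearest thing to a pass/fail criterion.
- **Analysis.** A reader might infer a planned test of ND against implant success. The analysis section relates each of them to lateralization and does not specify that test. This stands.
- **Existing data.** ND is tested by touch and pinprick, mapped at each visit, and rated by a pair of calibrated examiners, while implant pain is judged under torque or loading. ND status near the implant check is therefore already collected. This stands, and it makes the fix cheap. It does not supply a rule for attributing the pain.
- **Choice of criterion.** It is cited to a published study of the same kind of procedure, and a painful loaded implant can fairly be called unsuccessful. This stands against removing pain. It does not stand against showing what pain contributes.

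**Conclusion.** The point holds in one direction. As written, neuropathic pain can fail an implant that is immobile and radiographically sound, and the reported result would not reveal it. The opposite effect, from numbness, is small on the assumed values and zero if mobility or X-ray catches every failure.

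The size in this trial cannot be derived. Background calls ND common but gives no rate, and no rate for months 3 to 6 appears anywhere. A reader might turn assumed ND counts into a share of patients whose result is unreliable. The documents do not support that either: not every disturbance is painful, and a small mapped area need not involve every implant in a patient. The 11-point step per patient assumes exactly nine patients and a patient-level success measure, and the plan does not say whether the unit is the patient or the implant. The pass-rate ranges above rest wholly on the assumed values.

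This is an improvement in measurement and reporting. It does not show that the cited criterion is wrong.

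**What to change.** In Post-operative follow-up, record three components for each implant at each check: pain on torque or loading, mobility, and radiographic pathology. In Data management and statistical analysis, add the following:

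- Report each component separately.
- Report implant success twice, side by side: with the pain component, as in the cited source, and without it.
- Tabulate both by the patient's ND status (none, positive, negative) at the neurosensory assessment closest to the implant check. The monthly schedule already provides this.
- State that no relation between ND and implant success will be interpreted from the pain-inclusive version alone.

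The cost is one or two extra table rows and a second success figure beside the cited criterion, with no new test, visit or staff. If only an overall judgement was written down for each implant, the components would have to be taken from the visit notes. The change does not supply the missing cut-offs for ratchet stability, marginal bone loss or radiographic pathology, so the pain-free version is only as clear as those definitions.
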